9.5.2.2 Asthma Quality of Life Questionnaire (AQLQ) at Post-baseline Visits

[figure not shown]
AQLQ (Asthma Quality of Life Questionnaire) is a 32-item disease specific questionnaire designed to measure functional impairments that are most important to patients with asthma, with 7-point scale (1-totally limited/problems all the time, 7-not at all limited/no problems). It consists of 4 domains: symptoms, emotions, exposure to environmental stimuli and activity limitation. Mean score will be calculated for the four domains, as well as the overall quality-of-life score defined as the mean score of all 32 items.

For the overall score and each respective domain score, treatment group comparisons will be performed using the same MMRM model as specified for the primary analysis with baseline AQLQ as covariate.

The proportion of patients who achieve an improvement of at least 0.5 in the change from baseline in AQLQ (i.e. increase of AQLQ score of at least 0.5 from baseline) at post-baseline visits will be analyzed using the same logistic regression model via GEE specified for the ACQ-7 analysis except that baseline AQLQ will be used instead of the baseline ACQ-7.

The analyses on AQLQ will be based on the FAS for all post-baseline visits.

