Amendment 1	30-May-2018	
The amendment is largely based on the changes made in the Clinical Trial Protocol Amendment 5 (released 17-Jan-2018). More details about the rationale of the major changes are given in the section "Amendment 1". In summary, the following changes are implemented:
 
• The primary analysis will be conducted after all patients have completed the Week 26 assessments or discontinued from the study; changes are made in multiple sections with details given in Section 2.9.• Modified key secondary objective in Section 2.1.2 and updated analysis accordingly in Section 2.6.1.• Updated testing strategy for multiplicity due to the change in key secondary objective.• Sample size has been updated in Section 2.10.• Added the estimand statements in Section 2.1.• Modified the handling of missing items when calculating the ACQ-7 score and clarified the handling of missing ACQ-7 score for ACQ-responder analysis in Section 2.6.1.1.2.• Added ACQ-5 in Section 2.6.2.3.• Modified the handling of missing items in the AQLQ overall and domain scores in Section 2.6.2.8.• Added exposure-adjusted analyses of adverse events in Section 2.7.2.• Changed the analysis plan for glucose and potassium data.• Removed the logistic regression analysis for percentage of patients with at least one asthma exacerbation by exacerbation category and patients who permanently discontinued study medication due to asthma exacerbations in Section 2.6.2.7.• Extended the post-morning dose time window restriction in handling of spirometry measurements from 10-13 hours to 8-13 hours for b.i.d. regimens in Section 2.6.1.1.• Modified the multiple imputation method in tipping point analysis from monotone method to fully conditional specification method in Section 2.6.1.4 and Section 16.1.9.6.• Combined the imputation steps into one step for the ACQ responder analysis in Section 2.6.2.3 and Section 16.1.9.6.• Removed SAS code from SAP in Section 16.1.9.6 and included them in TFLs.• Removed the definitions of AEs of special interest from Section 2.7.2.• Updated criteria for Hy's law as per current guideline.• Added Section 3 for specifying analyses that will be reported outside of CSR.• Added Japanese and Chinese patients in subgroup analyses in Section 3.1.

Version	Date	Changes

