2.6.1.3 Multiplicity adjustment

To control the family-wise type-I error rate at the two-sided 5% significance level, a multiple testing procedure based on the trimmed Simes test as described in Brannath et al (2009) will be used. The family for the overall type-I error rate control contains three hypotheses: two hypotheses for the primary endpoint trough FEV₁ and one hypothesis for the key secondary endpoint ACQ-7. Denote the two hypotheses for the primary endpoint as H1 and H2 for comparing QMF149 150/160 µg vs. MF 400 µg and QMF149 150/320 µg vs. MF 800 µg respectively. Similarly, denote the hypothesis as H3 for the key secondary endpoint ACQ-7, for comparing QMF149 vs. MF combined doses.

Below is a brief description of the testing procedure based on the trimmed Simes test in Brannath et al (2009).

Let p₁, p₂, p₃ be the corresponding p-values (2-sided) of the three hypotheses of H1, H2, and H3.

Step 1: Retain both H1 and H2 if p_i ≤ 0.05 **AND** the observed treatment difference for the corresponding p_i is in the wrong direction (i.e. MF is performing better than QMF) for **ANY** i = 1, 2, stop here; otherwise go to Step 2.

Step 2: Reject H1 and H2 if p_i < 0.05 for **BOTH** i=1, 2 and go to Step 3; otherwise go to Step 4.

Step 3: Reject H3 if p₃ < 0.05 and stop;

Step 4: If neither Step 1 nor 2 applies, perform the Bonferroni test to H1 and H2. Thus reject H1 if p₁ < 0.025 or reject H2 if p₂ < 0.025 and stop.

For each of the three hypotheses, the corresponding testing statistics (estimated least square mean difference) follows normal distribution. Hence for H1 and H2, their corresponding testing statistics follow jointly bivariate normal distribution. Therefore this testing procedure controls the overall type I error rate at the 2-sided 0.05 level in the strong sense regardless if the bivariate normal distributions have positive or negative correlations as shown in Brannath et al (2009).

Other than the 3 treatment comparisons mentioned above for the primary and the key secondary endpoint, all other analyses will be performed at the nominal 2-sided 0.05 level (2-sided) without multiplicity adjustment.

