2.6.2 Analysis of secondary variables

Three treatment comparisons will be performed on all secondary variables: 1) QMF149 150/160 µg vs. MF 400 µg, 2) QMF149 150/320 vs MF 800 µg, 3) QMF149 150/320 µg vs. salmeterol xinafoate /fluticasone propionate 50/500 µg b.i.d.. The third comparison will be done on the key secondary variable too and on the primary variable as described below.

2.6.2.1 Comparison of QMF149 150/320 µg vs salmeterol xinafoate/fluticasone propionate 50/500 µg b.i.d. in term of trough FEV₁ at Week 26

QMF149 150/320 µg will be compared to active control (salmeterol xinafoate /fluticasone propionate 50/500 µg b.i.d.) for non-inferiority and – if non-inferiority is shown – for superiority on the primary endpoint. The same MMRM as specified above will be applied. The margin for non-inferiority is defined as 90 mL (see Appendix 12 of the study protocol for the estimation of non-inferiority margin). The result will be interpreted based on the two-sided 95% confidence interval (CI) of the treatment difference QMF149 – active control. The lower bound of the 95% CI is the difference that can be ruled out, i.e., if the lower bound of the 95% CI is larger than the non-inferiority margin of -90 mL, then QMF149 150/320 µg can be considered non-inferior to active control, and if the lower bound of the 95% CI is greater than 0, then QMF149 150/320 µg can be considered superior to active control with regard to trough FEV₁ at Week 26. Note that the comparison versus active control is not part of the confirmatory testing strategy.

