2.6.2.8 Quality of life as assessed by Asthma Quality of Life Questionnaire (AQLQ)

AQLQ is a 32-item disease specific questionnaire designed to measure functional impairments that are most important to patients with asthma, with a recall time of two weeks and each question to be answered on a 7-point scale (1-totally limited/problems all the time, 7-not at all limited/no problems). It consists of 4 domains:

- Symptoms = Mean of Items 6, 8, 10, 12, 14, 16, 18, 20, 22, 24, 29, 30 (12 items)
- Activity limitation = Mean of Items 1, 2, 3, 4, 5, 11, 19, 25, 28, 31, 32 (11 items)
- Emotional function = Mean of Items 7, 13, 15, 21, 27 (5 items)
- Environmental stimuli = Mean of Items 9, 17, 23, 26 (4 items)
- Overall Score = Mean of Items 1 to 32 (32 items)

[name], developer of AQLQ questionnaire suggests no more than 10% of missing data. This means that for a questionnaire of 32 items, no more than 3 items should be missing. Further, for the activity and symptom domains, the recommendation is no more than 1 missing value per domain, and for the emotional function and environmental stimuli domains, no missing responses at all. Missing individual items will be imputed similarly to missing items for ACQ-7.

For the overall score and each respective domain score, treatment group comparisons will be performed using the same MMRM model as specified for the primary analysis with baseline AQLQ as covariate. The post-baseline visits are scheduled for Weeks 4, 12, 26, 36, and 52.

The proportion of patients who achieve an improvement in the AQLQ (i.e., an increase in the AQLQ overall score of ≥ 0.5 from baseline) at post-baseline visits will be analyzed using the same logistic regression model via GEE as specified for the ACQ-7 analysis except that baseline AQLQ will be used instead of the baseline ACQ-7. The handling of missing data will also be the same as for ACQ-7, i.e., first missing continuous AQLQ values will be imputed using a MI method under MAR assumption. Then continuous AQLQ values will be converted into binomial responses and GEE method will be used to analyze the datasets and then the results from GEE method will be combined for the inference.

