2. After the imputation obtained in above step, for subjects in the two QMF149 treatment arms only, make the imputed value at Week 26 worse by a value of delta (i.e., subtract delta from the imputed value at Week 26). Note: delta = 0 represents the standard missing at random (MAR) based MI.
3. The final multiply-imputed dataset where all missing values are filled will be analyzed (by imputed dataset) using a linear model with treatment, age group, geographic region, baseline FEV₁, FEV₁ prior to inhalation, and FEV₁ 15 to 30 min post inhalation as predictors of trough FEV₁ at Week 26.
4. The results for the treatment effect from the 100 datasets will then be combined using Rubin's rule. If the combined results does not change the conclusion (i.e., the QMF149 treatment effect is still statistically significantly superior to MF), a larger delta will be chosen and Steps 1-4 will be repeated using the datasets from Step 1 until the tipping point is found (when $p > 0.05$).

- **Logistic regression analysis**

The proportions of patients who achieve a clinically relevant improvement in ACQ-7 (i.e., decrease of ACQ-7 score of at least 0.5 from baseline) at the scheduled post-baseline visits will be analyzed using logistic regression. The following steps will be performed for imputation of missing ACQ-7 data and following logistic regression analysis:

1. First, missing ACQ-7 values (continuous) at Visit 202, 204, 207, and 214 will be imputed sequentially using the MI method under MAR assumption. Missing values will be imputed separately for each treatment group using a model with age group (12 to 17, or ≥ 18 years), region, baseline ACQ value, FEV₁ prior to inhalation, FEV₁ within 15 to 30 min post inhalation of salbutamol/albuterol, and previous post-baseline ACQ-7 values as predictors for 100 times.
2. Continuous ACQ values will be converted into binomial responses (1 = an improvement of at least 0.5, 0 = no such improvement) and generalized estimating equation (GEE) method will be used to analyze the dataset (by imputed dataset). The GEE model will include terms for treatment, age group (12 to 17, or ≥ 18 years), region, visit, and treatment-by-visit interaction as fixed effects, and baseline ACQ-7, baseline-by-visit interaction, FEV₁ prior to inhalation and FEV₁ within 15 to 30 min post inhalation of salbutamol/albuterol (components of SABA reversibility) as covariates.

Combining results from 100 copies of original dataset:

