3. In the next step, results from each copy, obtained from GEE method will be combined for the inference using Rubin's rule. The SAS procedure PROC MIANALYZE will be used for combining the results considering the linear scale and then we will take exponential of combined result to obtain the odds ratio.

The combined effects of QMF149 (150/160 & 150/320 μg) and MF (400 & 800 μg) will be derived by weighting treatment groups equally.

The proportions of patients who achieve a clinically relevant improvement in AQLQ (i.e., decrease of AQLQ score of at least 0.5 from baseline) at the scheduled post-baseline visits (Visit 202, 204, 207, 210, and 214) will be analyzed using the same procedures as mentioned above for ACQ-7, except that baseline ACQ-7 is replaced by baseline AQLQ in all steps.

- **Linear Mixed Model Analysis of Covariance (ANCOVA)**

The following linear mixed ANCOVA model will be used for diary data summarized over 26 or 52 weeks:

Dependent variable = intercept + treatment + age group + region + baseline value + FEV₁ prior to inhalation + FEV₁ 15 to 30 min post inhalation + random effect of center nested within region + error.

Results will be presented with LSM and SE for treatment effects and LSM, SE, associated two-sided 95% confidence interval, and two-sided p-value for all relevant treatment contrasts.

- **Cox regression analysis**

A Cox proportional hazards regression model will be applied in time-to-event analyses to test the null-hypothesis $H_0: \lambda_{\text{QMF}}(t) / \lambda_{\text{Control}}(t) = 1$, where $\lambda(t)$ is the hazard function for the failure time of patients treated with QMF and the control group, respectively. The Cox regression

model will be stratified by age group (12 – 17, ≥ 18 years) and will include terms for treatment, region, history of asthma exacerbation in the 12 months prior to screening (Yes, No), FEV₁ prior to inhalation and FEV₁ within 15 to 30 min post inhalation of salbutamol/albuterol (components of SABA reversibility).

Results will be presented with adjusted hazard ratios for treatment group comparisons and associated 95% confidence intervals and two-sided p-values. P-values will be obtained from the Wald chi-squared statistic testing the null-hypothesis that the parameter estimate for the respective treatment effect is 0 (then the hazard ratio is $\exp(0) = 1$).

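### SAP Appendix 16.1.9.6 defines AQLQ improvement as a decrease of at least 0.5; the scale, SAP 2.6.2.8 and protocol 9.5.2.2 require an increase

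*SAP*

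**What the plan says.** The AQLQ responder analysis is described in three places.

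- **SAP 2.6.2.8** gives the scale anchors as "1-totally limited/problems all the time, 7-not at all limited/no problems" and defines the responder by "an increase in the AQLQ overall score of ≥ 0.5 from baseline". It then points to the logistic model via GEE, with multiple imputation, that is used for ACQ-7.
- **Protocol 9.5.2.2** gives the same anchors and also defines the responder by an "increase of AQLQ score of at least 0.5 from baseline".
- **SAP Appendix 16.1.9.6**, under logistic regression, describes the same analysis as the proportion of patients with a "clinically relevant improvement in AQLQ (i.e., decrease of AQLQ score of at least 0.5 from baseline". It applies the ACQ-7 steps to AQLQ with one stated substitution: the AQLQ baseline takes the place of the ACQ-7 baseline.

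Step 2 of those ACQ-7 steps codes the binary outcome as "1 = an improvement of at least 0.5, 0 = no such improvement", without naming a direction.

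**The concern.** One planned analysis has two opposite definitions in the same SAP. The version in the step-by-step methods section is the one that contradicts the scale. A programmer working from 16.1.9.6 would flag as responders the patients whose quality of life fell by at least 0.5, and the output would be labelled as improvement. If QMF149 improves quality of life relative to its comparator, the reported odds ratio would tend to point the wrong way.

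The SAP cannot show which rule was programmed, because its amendment history records that the code was moved out: "Removed SAS code from SAP in Section 16.1.9.6 and included them in TFLs". The appendix is also headed as Clinical Study Report Appendix 16.1.9, so the wrong definition would appear in the report's own methods documentation.

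**Working it through.** The plan states no figure that depends on this point, so the check is a comparison of texts, followed by an illustration of the effect.

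**1. Direction of each scale**

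| Instrument | Best | Worst | Improvement is | Source |
|---|---|---|---|---|
| AQLQ | 7 | 1 | an increase | SAP 2.6.2.8; protocol 9.5.2.2 |
| ACQ-7 | 0 | 6 | a decrease | protocol 6.4.2.1; SAP 2.6.1.1.2 |

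SAP 16.1.9.3.3 defines change as the post-baseline value minus the baseline value, so no sign convention turns an AQLQ decrease into an improvement. The threshold of 0.5 is the same everywhere (also in protocol 6.4.2.2). Only the direction conflicts.

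**2. Probable source of the error**

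The ACQ-7 paragraph earlier in the same part of 16.1.9.6 has a parallel sentence with a decrease, which is right for ACQ-7. Carry-over into the AQLQ paragraph is an inference; the error does not depend on it.

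**3. What each rule counts**

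Take a baseline AQLQ of 4.0.

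| Post-baseline score | Change | Responder if change ≥ +0.5 | Responder if change ≤ −0.5 |
|---|---|---|---|
| 4.6 | +0.6 | yes | no |
| 4.2 | +0.2 | no | no |
| 3.4 | −0.6 | no | yes |

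The two rules count opposite tails and are not complements, because patients in the middle are non-responders under both. A result produced under the wrong rule could therefore not be repaired by inverting the odds ratio. The analysis would have to be re-run.

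**4. Illustration of the effect**

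The documents give no AQLQ mean or SD, so these inputs are assumptions: normally distributed change, SD 0.8, mean +0.50 on MF and +0.65 on QMF149. Φ is the standard normal distribution function.

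Correct rule, P(change ≥ 0.5) = 1 − Φ((0.5 − mean)/SD):
- MF: 1 − Φ(0) = 50.0%
- QMF149: 1 − Φ(−0.1875) = 57.4%
- Odds ratio: (0.574/0.426)/(0.500/0.500) = 1.35

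Appendix rule, P(change ≤ −0.5) = Φ((−0.5 − mean)/SD):
- MF: Φ(−1.25) = 10.6%
- QMF149: Φ(−1.4375) = 7.5%
- Odds ratio: (0.0753/0.9247)/(0.1056/0.8944) = 0.69

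Non-responders under both rules: 100 − 50.0 − 10.6 = 39% on MF and 100 − 57.4 − 7.5 = 35% on QMF149. Inverting 0.69 gives about 1.45, not 1.35, which confirms step 3.

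Over MF means of 0.3 to 0.7, differences of 0.10 to 0.20 and SDs of 0.8 to 1.0, the correct odds ratio runs from 1.17 to 1.50 and the appendix odds ratio from 0.58 to 0.84. The two ranges lie on opposite sides of 1.

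**5. Reach**

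The appendix names five visits (202, 204, 207, 210 and 214). SAP 2.6.2 states that "Three treatment comparisons will be performed on all secondary variables". That makes 5 × 3 = 15 odds ratios. SAP 2.6.1.3 places them outside the confirmatory family: apart from the three confirmatory comparisons, "all other analyses will be performed at the nominal 2-sided 0.05 level".

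**The case against.** The strongest reply is that the documents already show which direction is right. SAP section 1 says that the data will be analysed according to protocol Section 9, and protocol 9.5.2.2 belongs to it. SAP 2.6.2.8, the section on this endpoint, agrees with the protocol. SAP 2.1.5, which lists changes to planned analyses, reports none for AQLQ. Step 2 speaks only of improvement, so a programmer who starts from 2.6.2.8 would code it correctly. A reversed flag would probably also be noticed: under the assumptions above, MF response would be 10.6% instead of 50.0%, and the odds ratio would run against the AQLQ MMRM.

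All of this stands as evidence of what was intended. It leaves the wrong rule in the operative methods text, and detection by a careful programmer is not a safeguard that the plan provides.

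Three smaller points are fair:

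- The AQLQ responder proportion is not itself a listed objective. The listed objective is AQLQ over 52 weeks, so this is a further analysis of a secondary variable.
- The count of three comparisons may be low. The combined QMF149 versus MF effect is part of the ACQ-7 procedure that the AQLQ paragraph reuses.
- The odds ratios come from a simple normal model, not from the planned imputation and adjusted GEE. They show direction only.

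**Conclusion.** The concern holds. The definition in SAP 16.1.9.6 contradicts the AQLQ scale, the SAP's own endpoint section and the protocol, and if followed it would report worsening as improvement. This conclusion rests on the text alone and needs no assumption. Only the illustrative odds ratios (1.35 against 0.69) depend on assumed means and SD.

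The consequence is confined to the AQLQ responder analysis. The continuous AQLQ analysis, trough FEV₁, ACQ-7, the multiplicity procedure and the sample size do not change. It should be fixed, but it does not threaten the trial's main conclusions. Nothing in the documents shows that the wrong rule was actually programmed.

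**What to change.** In the AQLQ paragraph of SAP 16.1.9.6, replace the parenthetical definition with an increase of at least 0.5 from baseline in the AQLQ overall score, which matches 2.6.2.8 and also restores its reference to the overall score. Step 2 can stay as it is: 1 means improvement, which for AQLQ is a change of +0.5 or more. Then check the derived AQLQ responder flag, the output shells and the TFL code against this definition before the analysis is run.

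The cost is one phrase in the SAP and a short programming check. No new analysis choice is introduced.
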